## 6. Statistical Analysis

### 6.1. General Considerations

Please refer to Table 8 in the protocol for Schedule of Events (SoE).

The following follow-up periods for safety analyses and Concomitant Medications will be used:

- Overall follow-up period (throughout the study): from the day of the IP injection (Day 1) to the earliest date of (study completion, discontinuation from the study, or death)
- Up to 28 days follow-up period: from the day of the IP injection (Day 1) to the earliest date of (the day of the IP injection and 27 subsequent days, discontinuation from the study, or death)
- After 28 days follow-up period: from the 28 days after the IP injection to the earliest date of (study completion, discontinuation from the study, or death)
- 7-day follow-up period: from the day of the IP injection (Day 1) to the earliest date of (Day 7 after the IP injection, discontinuation from the study, or death)

**Continuous variables** will be summarized using the following descriptive summary statistics: the number of subjects (n), mean, standard deviation (SD), median, minimum (min), and maximum (max).

**Categorical variables** will be summarized using counts and percentages.

**Baseline value**, unless specified otherwise, is defined as the most recent non-missing measurement (scheduled or unscheduled) collected before the dose of IP in this study.

For the summary statistics of all numerical variables unless otherwise specified, the display precision will follow programming standards. Please see [Appendix A](#) for variable display standards.

When count data are presented, the percentage will be suppressed when the count is zero in order to draw attention to the non-zero counts. A row denoted “Missing” will be included in count tabulations where specified on the shells to account for dropouts and missing values. The denominator for all percentages will be the number of subjects in the treatment group within the analysis set of interest, unless otherwise specified.

**End of Study** (EoS) for the participants is defined as any of completion of the study if the participant has completed all phases of the study including the last scheduled procedure as shown in the SoE (Table 8 in the protocol), discontinuation of study due to any reason, death, and termination of the trial by the Sponsor.

**Pre-booster SARS-CoV-2 status** is determined by using virologic and serologic evidence of SARS-CoV-2 infection on or before Day 1 (pre-booster).

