### **6.2.1. Subject Disposition**

The number and percentage of subjects in the following categories will be summarized by treatment group as defined in [Section 6.1](#) based on the Randomized/Enrolled Set:

- Randomized Set (Part A only)

- Enrolled Set (Part B only)
- FAS
- PPIS
- PPIS-Neg
- Safety Set
- Solicited Safety Set

Percentages will be based on the number of subjects in the treatment group within the Randomized/Enrolled Set (as randomized/enrolled). For Solicited Safety Set, the percentage will be based on the number of subjects in the treatment group within the Safety Set (as treated).

Summary of reasons for subjects excluded from the PPIS, PPIS-Neg analysis sets will also be provided.

The number of subjects in the following categories will be summarized based on subjects screened:

- Number of subjects screened
- Number and percentage of screen failure subjects and the reason for screen failure

The percentage of subjects who screen failed will be based on the number of subjects screened. The reason for screen failure will be based on the number of subjects who screen failed.

The number and percentage of subjects in each of the following disposition categories will be summarized by treatment group based on the Randomized/Enrolled Set:

- Received IP
- Completed study
- Prematurely discontinued the study and the reason for discontinuation

This study treatment consists of a single booster, thus discontinuation from study treatment is not applicable to this study. A subject is considered to have completed the study if he or she has completed the study including the last scheduled procedure as shown in the SoE (Table 8 in the Protocol).

A subject disposition listing will be provided, including the information about ICF completion, IPs received, Study completion and EoS reasons if discontinuation from the study. A separate listing will be provided for screen failure subjects with reasons for screen failure.

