## 6.6. Efficacy Analysis

Part A and B:

SARS-CoV-2 infection cases, including both symptomatic and asymptomatic cases, and COVID-19 cases, defined with both CDC and Moderna mRNA-1273 P301 study, by treatment group will be summarized.

Pre-booster SARS-CoV-2 status is described in [Section 6.1](#).

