### 6.6.1. Endpoint Definition/Derivation

#### 6.6.1.1. Derivation of SARS-CoV-2 Infection

SARS-CoV-2 infection is considered as either positive status of COVID-19 or asymptomatic SAS-CoV-2 infection for participants with negative pre-booster SARS-CoV-

2 status. It will be counted starting 14 days after the dose of IP SARS-CoV-2 infection will be defined in participants with negative pre-booster SARS-CoV-2 status by either:

- bAb levels against SARS-CoV-2 nucleocapsid protein negative at Day 1 that becomes positive after the IP injection, OR
- Positive RT-PCR after the dose of IP.

The date of documented infection will be the earlier of:

- Date of positive post-baseline RT-PCR result, or
- Date of positive post-baseline serology test result

The time to the first SARS-CoV-2 infection will be calculated as:

Time to the first SARS-CoV-2 infection = Date of the first documented infection – Date of the IP injection + 1.

Cases will be counted starting 14 days after the IP injection. They will be summarized by treatment group.

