#### **6.6.1.2. Derivation of Asymptomatic SARS-CoV-2 Infection**

The incidence of asymptomatic SARS-CoV-2 infection measured by RT-PCR of nasopharyngeal swabs and/or serology tests obtained at post-baseline visits is counted starting 14 days after the IP injection in participants with negative pre-booster SARS-CoV-2 status.

Asymptomatic SARS-CoV-2 infection is identified by absence of symptoms with positive status per RT-PCR or serology tests at a post-baseline visit, specifically:

- Absent of COVID-19 symptoms AND at least one from below:
- bAb levels against SARS-CoV-2 nucleocapsid protein negative at Day 1 that becomes positive after the IP injection, OR
- Positive RT-PCR test after the IP injection.

The date of the asymptomatic infection is the earlier date of positive serology test result based on bAb specific to SARS-CoV-2 nucleocapsid, or positive post-baseline RT-PCR, with absence of symptoms.

The time to the asymptomatic SARS-CoV-2 infection will be calculated as:

Time to the asymptomatic SARS-CoV-2 infection = Date of the asymptomatic SARS-CoV-2 infection – Date of the IP injection + 1.

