#### 6.6.1.3. Derivation of COVID-19

The incidence of the first occurrence of symptomatic COVID-19 infection cases is recorded starting 14 days after the injection. Surveillance for COVID-19 will be conducted through monthly contact and scheduled blood collection. Subjects reporting COVID-19 symptoms will be arranged an illness visit to collect an NP swab.

Two definitions of the COVID-19 will be evaluated:

1. Primary case definition per the Phase 3 study (mRNA-1273-P301): Cases are defined as participants meeting clinical criteria based on both symptoms for the COVID-19 and positive RT-PCR test results as described in [Table 2-1](#).
2. Secondary case definition based on CDC criteria: The presence of one of the CDC-listed symptoms ([Table 2-2](#)) and a positive RT-PCR test on a respiratory sample.

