#### **6.6.2. Analysis Method**

The number and percentage of subjects who had each type of event (i.e., an asymptomatic or a symptomatic SARS-CoV-2 infection) will be summarized with FAS.

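### SAP 6.6.2 sets infection cases that only pre-booster-negative participants can supply over the whole FAS arm, so the percentages understate risk in those who can be cases (minor, exploratory).

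*SAP*

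**What the plan says.** **Who can be a case.** SAP 6.6.1.1 states that "infection will be defined in participants with negative pre-booster SARS-CoV-2 status by either" of two laboratory criteria. SAP 6.6.1.2 says that asymptomatic infection "is counted starting 14 days after the IP injection in participants with negative pre-booster SARS-CoV-2 status". Under SAP 6.1, negative status requires both a negative RT-PCR and a negative nucleocapsid serology on or before Day 1.

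**What is reported.** SAP 6.6 plans a summary by treatment group of "SARS-CoV-2 infection cases, including both symptomatic and asymptomatic cases, and COVID-19 cases". SAP 6.6.2 gives the method as number and percentage of subjects with each event type: "an asymptomatic or a symptomatic SARS-CoV-2 infection) will be summarized with FAS".

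**Which denominator.** SAP 6.1 sets a general rule: "The denominator for all percentages will be the number of subjects in the treatment group within the analysis set of interest, unless otherwise specified". SAP 5.3 defines the FAS as everyone randomized or enrolled who was dosed, without regard to infection status. SAP 4.1 admits people with prior infection and sets no cap on their share.

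**Symptomatic disease.** SAP 6.6.1.3 says "The incidence of the first occurrence of symptomatic COVID-19 infection cases is recorded starting 14 days after the injection" and does not mention pre-booster status. The opening of 6.6.1.1 is less clear: "SARS-CoV-2 infection is considered as either positive status of COVID-19 or asymptomatic SAS-CoV-2 infection for participants with negative pre-booster" status. The closing condition may apply to asymptomatic infection alone or to COVID-19 as well.

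**The concern.** The numerator and denominator come from different populations. Participants who were positive at baseline, or whose baseline RT-PCR or serology is missing, are excluded from the case count by definition but remain in the FAS denominator. The result is not the risk among those who can be cases. Nor is it the proportion of all dosed participants who became infected, because new infections in baseline positives are left out of the numerator.

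Two things follow. Every percentage in these rows is too low as a measure of risk in negatives, by a factor that depends on how many people in the arm were not negative. And if that share differs between arms, the comparison is distorted. In Part A, randomization equalizes the share on average. In Part B the two arms are enrolled one after the other (protocol 5.2), so the prevalence of prior infection could differ between them.

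**Working it through.** The documents state no infection rate, expected case count or share of participants positive at baseline, so there is no planned figure to reproduce. The only input from the documents is the arm size, up to 70 (protocol 8.3, SAP 4.2). The other two inputs are assumed:

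- q, the share of the FAS arm not classed as pre-booster negative: 5%, 20%, 40%
- r, the true risk among negatives: 10%, 30%, 50%

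**Formula.** Let N be the FAS arm size. Negatives = N(1 − q) and cases = r × N(1 − q). Printed percentage = cases / N = r(1 − q).

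| r in negatives | q = 5% | q = 20% | q = 40% |
|---|---|---|---|
| 10% | 9.5% | 8.0% | 6.0% |
| 30% | 28.5% | 24.0% | 18.0% |
| 50% | 47.5% | 40.0% | 30.0% |

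**In counts.** With 14 cases in an arm of 70, the table prints 14/70 = 20.0%. The risk among negatives would be:

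- 66 negatives (q = 4/70 = 5.7%): 14/66 = 21.2%
- 56 negatives (q = 20%): 14/56 = 25.0%
- 42 negatives (q = 40%): 14/42 = 33.3%

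**Between arms, equal q.** The factor (1 − q) cancels in a ratio but not in a difference.

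- True 30% versus 15%: the ratio stays 2.0. The 15-point difference prints as 15 × 0.95 = 14.25, 15 × 0.80 = 12.0 or 15 × 0.60 = 9.0 points.
- True 10% versus 5%: the 5-point difference prints as 4.75, 4.0 or 3.0 points.

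**Between arms, unequal q and identical true risk.** The printed ratio is (1 − q1)/(1 − q2) when it should be 1. For a 10-point gap in q:

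- 5% versus 15%: 0.95/0.85 = 1.12
- 20% versus 30%: 0.80/0.70 = 1.14
- 30% versus 40%: 0.70/0.60 = 1.17

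The false difference is r(q2 − q1): 1, 3 or 5 points at r = 10%, 30% or 50%.

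**Can the right figure be recovered?** Almost exactly. SAP 6.2.2 tabulates pre-booster status by arm in the Safety Set. By SAP 5.3 and 5.6 the Safety Set and FAS have the same membership rule. They differ only in arm assignment, for anyone given the wrong product. Dividing the case count by the negatives in that table gives the risk.

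**The case against.** The best counter-argument is that 6.6.2 names an analysis set, not a denominator. The 6.1 rule gives way where something else is specified, and 6.6.1.2 speaks of incidence counted in participants with negative status, which could be taken as naming the population at risk. SAP 6.6 also refers the reader back to the definition of pre-booster status. A programmer could produce a negatives-only table and believe it followed the SAP.

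That reading is possible but weaker. The sentence in 6.6.1.2 says who is counted as a case and sets no base for a percentage. Where the SAP wants a different base it says so, as in 6.2.1 for the Solicited Safety Set and for screen failures, and for immunogenicity it creates a negatives-only set. Section 6.6 does neither. Even if the intention was negatives only, the text allows two different percentages.

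Some further objections do stand:

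- 6.6.2 names asymptomatic and symptomatic infection. Its application to the combined infection row is a natural inference, while the asymptomatic row is explicit.
- 6.6.1.3 is silent on pre-booster status, and silence need not contradict 6.6.1.1. COVID-19 in a baseline positive could count as COVID-19 and not as infection under 6.6.1.1. If so, the full FAS is the right base for the COVID-19 row.
- The size rests wholly on assumed q.
- A corrected denominator would not remove any calendar-time difference in exposure between the Part B arms.

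**Conclusion.** The concern holds. Read with the 6.1 default, SAP 6.6.2 produces percentages for SARS-CoV-2 infection and asymptomatic infection that understate risk among those who can be cases whenever an arm includes anyone not classed as negative. The direction is certain and the relative shortfall equals q. Its size cannot be known from the documents; 5% to 40% is an assumed range.

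The same problem reaches the symptomatic row only if 6.6.1.1 is meant to limit COVID-19 to negatives.

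Severity is minor. Protocol 8.5.2 plans no pre-specified efficacy analysis and says the infection analyses may be done; the SAP, which takes precedence over the protocol on methods, says they will be summarized, so the tables should be expected. No hypothesis is tested, case counts are right, and a reader who knows to do so can rescale from the baseline table.

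**What to change.** In SAP 6.6.2, state that percentages for SARS-CoV-2 infection and asymptomatic infection use FAS participants with negative pre-booster status, as defined in 6.1, and show that n for each arm. In 6.6.1.3, state whether pre-booster-positive participants can be COVID-19 cases, and match the denominator: negatives if they cannot, the full FAS if they can.

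The cost is one sentence in each section and changed denominators in the table shells. No new data are needed. The visible effect is smaller denominators, 70(1 − q) = 66.5, 56 or 42 instead of 70 at q = 5%, 20% or 40%, and correspondingly higher percentages.

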#### **6.7. Primary Analysis**

The primary analysis of safety and immunogenicity will be conducted after Part A participants have completed their Day 29 visit assessments. All data relevant to the primary analysis through Day 29 will be cleaned (as clean as possible) and locked. The primary analysis will be performed by a separate team of unblinded programmers and statisticians. The analysis, including any case of COVID-19, will be presented by treatment group. With the exception of appropriately delegated unblinded study staff, vaccine administrators, and monitors, all personnel involved in the conduct of the trial will remain blinded to individual treatment assignment until unblinding. Investigators will be blinded until after the final database lock for final analysis.

#### **6.8. Interim Analysis**

The interim analysis of safety and immunogenicity will be conducted after Part B participants have completed their Day 29 visit assessments. The interim analysis will be performed by study team programmers and statisticians.

## **6.9. Final Analysis**

The final analysis of all endpoints will be performed after all participants (Part A and Part B) have completed all planned study procedures. Results of this analysis will be presented in a final CSR, including individual listings. The final CSR will include full analyses of all safety and immunogenicity data through Day 366 (Month 12).

## **6.10. Data and Safety Monitoring Board**

An independent data and safety monitoring board (DSMB), composed of external and independent subject matter experts and an unblinded statistician, will conduct unblinded reviews of safety data on an ad hoc basis if any pause rule is met or as requested by the safety oversight and/or the internal safety team.

## **6.11. Cardiac Event Adjudication Committee**

An independent cardiac event adjudication committee (CEAC) that includes pediatric and adult cardiologists will review suspected cases of myocarditis and pericarditis to determine if they meet CDC criteria of “probable” or “confirmed” events, and to assess severity.

## **7. Changes from Planned Analyses in Protocol**

There are no changes from planned analyses in protocol.

## 9. List of Appendices

### 9.1. Appendix A Standards for Safety and Immunogenicity Variable Display in TFLs

**Continuous Variables:** The precision for continuous variables will be based on the precision of the data itself. The mean and median will be presented to one decimal place more than the original results; the SD will be presented to two decimal places more than the original results; the minimum and maximum will be presented to the same precision as the original results.

**Categorical Variables:** Percentages will be presented to 1 decimal place.

### 9.2. Appendix B Analysis Visit Windows for Safety and Immunogenicity Analysis (Part A and Part B)

Safety and Immunogenicity Analysis will be summarized using the following analysis visit window for post injection assessments:

Step 1: If the safety and immunogenicity assessments are collected at scheduled visit, i.e. nominal scheduled visit, the data collected at scheduled visit will be used.

Step 2: If the safety and immunogenicity assessments are not collected at the scheduled visit, assessments collected at unscheduled visit will be used using the analysis visit windows described in [Table 3](#) below.

If a subject has multiple assessments within the same analysis visit, the following rule will be used:

- If multiple assessments occur within a given analysis visit, the assessment closest to the target study day will be used.
- If there are 2 or more assessments equal distance to the target study day, the last assessment will be used.

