At the vaccination visit (Day 1), participants will be instructed how to document and report solicited ARs in a provided electronic diary (eDiary). Solicited ARs will be assessed for 7 days after the injection (the day of injection and the following 6 days), and unsolicited AEs will be assessed for 28 days after each injection. Medically attended AEs, SAEs, AESIs, and AEs leading to withdrawal will be assessed throughout the study. All participants will be tested for the presence of SARS-CoV-2 anti-nucleocapsid antibodies at Days 1, 29, 181, and 366, as well as by nasopharyngeal (NP) swab RT-PCR on Days 1, 29, 181, and 366. Active surveillance for intercurrent or breakthrough SARS-CoV-2 infection will occur throughout the study and be reported as AEs (confirmed symptomatic infections will be reported as MAAEs if not an SAE). Symptomatic infection will be prompted by signs and symptoms meeting the US Centers for Disease Control and Prevention ([CDCb 2021](#)) case definition for COVID-19 (05 Aug 2020 or most recent), as well as the clinical suspicion of the site investigator. Participants will be asked to contact the study site to arrange for a prompt, thorough, and careful assessment. Participants will

have blood sampled at scheduled study site visits (Days 1, 15, 29, 181, and 366) during the study for immunogenicity assessments or other medical concerns according to the investigator's judgment.

Participants may experience AEs, including symptoms of COVID-19, that necessitate an unscheduled visit. There may also be situations in which the investigator asks a participant to report for an unscheduled visit following the report of an AE. Additional examinations may be conducted at these visits as necessary to ensure the safety and well-being of participants during the study. Electronic case report forms (eCRFs) should be completed for each unscheduled visit. In addition, participants may have blood sampled at unscheduled visits for acute respiratory symptoms.

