## 7. STUDY ASSESSMENTS AND PROCEDURES (PART A AND PART B)

Before performing any study procedures, all potential participants will sign an informed consent form (ICF) (as detailed in [Section 10.2.6](#)). Participants will undergo study procedures at the time points specified in the SoE ([Table 8](#)). A participant can also be seen for an unscheduled visit at any time during the study. An unscheduled visit may be prompted by reactogenicity issues, illness visit criteria for COVID-19, or new or ongoing AEs. The site also has the discretion to make reminder telephone calls or send text messages to inform the participant about visits, review eDiary requirements, or follow-up on ongoing or outstanding issues.

The study site staff are responsible for ensuring that participants comply with the allowed study visit windows. If a participant misses a visit, every effort should be made to contact the participant and complete a visit within the defined visit window specified in the SoE ([Table 8](#)). If a participant does not complete a visit within the time window, that visit will be classified as a missed visit and the participant will continue with subsequent scheduled study visits. All safety requirements of the missed visit will be captured and included in the subsequent visit.

In accordance with “FDA Guidance on Conduct of Clinical Trials of Medical Products during COVID-19 Public Health Emergency” ([DHHS 2020](#)), investigators may convert study site visits to home visits or telemedicine visits with the approval of the Sponsor. Such action should be taken to protect the safety and well-being of participants and study site staff or to comply with state or municipal mandates.

General considerations for study assessments and procedures include the following:

- Protocol waivers or exemptions are not allowed. The study procedures and their timing must be followed as presented in the SoE ([Table 8](#)). Adherence to the study design requirements is essential and required for study conduct.
- Immediate safety concerns should be discussed with the Sponsor immediately upon occurrence or awareness to determine if the participant should continue participation in the study.

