### 7.3.6. Assessment for SARS-CoV-2 Infection

Participants will have NP samples collected for SARS-CoV-2 testing at time points specified in the SoE ([Table 8](#)).

A study illness visit or a consultation will be arranged within 24 hours or as soon as possible to collect an NP swab ([Table 8](#), Unscheduled Visit [UNS]) to ascertain the presence of SARS-CoV-2 via RT-PCR if a participant experiences any of the following (the presence of any one of these symptoms lasting at least 48 hours [except for fever and/or respiratory symptoms]):

- Signs or symptoms of SARS-CoV-2 infection as defined by the CDC ([CDCb 2021](#)), including:
  - Fever (temperature  $\geq 38.0^{\circ}\text{C}$  [ $100.4^{\circ}\text{F}$ ]) or chills (of any duration, including  $\leq 48$  hours)
  - Cough (of any duration, including  $\leq 48$  hours)
  - Shortness of breath and/or difficulty breathing (of any duration, including  $\leq 48$  hours)
  - Fatigue
  - Muscle or body aches
  - Headache
  - New loss of taste and/or smell
  - Sore throat, congestion, or runny nose
  - Nausea or vomiting
  - Diarrhea
- MAAE suggesting a SARS-CoV-2 infection
- Clinical or radiographical evidence of pneumonia

Additionally, clinical information will be carefully collected to evaluate the severity of the clinical case. All findings will be recorded in the eCRF.

It is important to note that some of the symptoms of COVID-19 overlap with solicited systemic ARs that are expected after vaccination with mRNA-1273 or mRNA-1283 (eg, myalgia, headache, fever, and chills). During the first 7 days after vaccination, when these solicited ARs are common, investigators should use their clinical judgment to decide whether an NP swab should be collected. The collection of an NP swab prior to the Day 1 vaccination can help ensure

that cases of COVID-19 are not overlooked. Any study participant reporting respiratory symptoms during the 7-day period after vaccination should be evaluated for COVID-19.

If scheduled, a study site illness visit may include additional assessments such as medical history, physical examination, and blood sampling for clinical laboratory testing. The NP swab sample may be tested by multiplex RT-PCR for respiratory viruses besides SARS-CoV-2 to evaluate the severity of the clinical case. Radiologic imaging studies may be conducted. Blood samples will be collected at all illness visits for potential future immunologic assessment of SARS-CoV-2 infection.

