## 10.1. APPENDIX 1: Schedule of Events

**Table 8: Schedule of Events for Part A and Part B**

Visit Number	Screening 	V1 		V2	V3	V4			V5			V6	UNS
Type of Visit	C	C	SC	C	C	C	SFU	SFU	C	SFU	SFU	C	C
Month Time Point	M0	M0			M1	M3	eDiary	SC	M6	eDiary	SC	M12	--
Study Visit Day	Screening 	D1 	D8	D15	D29	D90	Every 2 weeks D36-D162 	Every 2 weeks D43-D169	D181	Every 2 weeks D202-D342 	Every 2 weeks D209-D349	D366	
Window Allowance (Days)	-7	0	+3	±3	-7 to +3	±7	±2	±3	±14	±2	±3	±14	--
Days Since Most Recent Injection		0	7	14	28	89	--		180	--		365	--
Informed consent form, demographics, concomitant medications, medical history	X												
Study injection (including 30-minute post-vaccination observation period)		X											
Confirm participant meets inclusion and exclusion criteria	X	X											
Physical examination including vital signs 	X	X			X				X			X	X
Pregnancy testing		X											

Visit Number	Screening 	V1 		V2	V3	V4			V5			V6	UNS
Type of Visit	C	C	SC	C	C	C	SFU	SFU	C	SFU	SFU	C	C
Month Time Point	M0	M0			M1	M3	eDiary	SC	M6	eDiary	SC	M12	--
Study Visit Day	Screening 	D1 	D8	D15	D29	D90	Every 2 weeks D36-D162 	Every 2 weeks D43-D169	D181	Every 2 weeks D202-D342 	Every 2 weeks D209-D349	D366	
Window Allowance (Days)	-7	0	+3	±3	-7 to +3	±7	±2	±3	±14	±2	±3	±14	--
Days Since Most Recent Injection		0	7	14	28	89	--		180	--		365	--
Blood for SARS-CoV-2 serology (anti-nucleocapsid antibody)		X			X	X			X			X	X
Blood for humoral immunogenicity 		X		X	X	X			X			X	X
Blood (PBMCs) for cellular immunogenicity		X			X				X			X	
Nasopharyngeal swab sample for SARS-CoV-2 		X			X	X			X			X	X
eDiary activation for recording solicited adverse reactions (7 days)		X											
Review of eDiary			X				X			X			
Follow-up safety calls 			X					X			X		

Visit Number	Screening 	V1 		V2	V3	V4			V5			V6	UNS
Type of Visit	C	C	SC	C	C	C	SFU	SFU	C	SFU	SFU	C	C
Month Time Point	M0	M0			M1	M3	eDiary	SC	M6	eDiary	SC	M12	--
Study Visit Day	Screening 	D1 	D8	D15	D29	D90	Every 2 weeks D36-D162 	Every 2 weeks D43-D169	D181	Every 2 weeks D202-D342 	Every 2 weeks D209-D349	D366	
Window Allowance (Days)	-7	0	+3	±3	-7 to +3	±7	±2	±3	±14	±2	±3	±14	--
Days Since Most Recent Injection		0	7	14	28	89	--		180	--		365	--

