### **5.4. Per-Protocol (PP) Immunogenicity Set (PPIS)**

The PPIS consists of all participants in the FAS who receive the planned dose of IP, have pre-booster and Day 29 neutralizing antibody data against prototype virus strain, have no previous HIV infection and who have no major protocol deviations that impact key or critical data. Participants will be included in the treatment group to which they were randomized/enrolled. The PPIS will be used as the sensitivity analysis set for analyses of immunogenicity.

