Positive SARS-CoV-2 status at pre-booster baseline is defined as a positive RT-PCR test for SARS-CoV-2, and/or a positive serology test based on bAb specific to SARS-CoV-2 nucleocapsid on or before Day 1.

Negative SARS-CoV-2 status at pre-booster baseline is defined as a negative RT-PCR test for SARS-CoV-2 and a negative serology test based on bAb specific to SARS-CoV-2 nucleocapsid on or before Day 1.

**Study day relative to the injection** will be calculated as below:

- a) study day prior to the injection will be calculated as: date of assessment/event – date of the injection
- b) study day on or after the date of the injection will be calculated as: date of assessment/event – date of the injection + 1

**For calculation regarding antibody levels/titers**, antibody values reported as below the lower limit of quantification (LLOQ) will be replaced by  $0.5 \times \text{LLOQ}$ . Values that are greater than the upper limit of quantification (ULOQ) will be converted to the ULOQ if actual values are not available. Missing results will not be imputed.

**Unscheduled visits:** Unscheduled visit measurements will be included in the analyses as follows:

- In scheduled visit windows per specified visit windowing rules
- In the derivation of baseline/last on-treatment measurements
- In the derivation of maximum/minimum on-treatment values and maximum/minimum change from baseline values for safety analyses
- In individual subject data listings

**Visit window rules:** The analysis visit windows for protocol-defined visits are provided in [Appendix B](#).

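### An unscheduled sample from as late as Day 59, including one drawn during COVID-19, can stand in for a missing Day 29 titre, and nothing now written clearly keeps it out of the primary analysis

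*SAP*

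**What the plan says.** SAP Section 9.2 (Appendix B) assigns samples in two steps. Step 1 takes the sample from the nominal scheduled visit. Step 2 applies when assessments "are not collected at the scheduled visit, assessments collected at unscheduled visit will be used using the analysis visit windows" of Table 3. For humoral immunogenicity, Table 3 gives Day 15 the range 2 to 22 and Day 29 the range 23 to 59. If several samples qualify, the one nearest the target day is used. SAP Section 6.1 states the same rule for unscheduled measurements in general: "In scheduled visit windows per specified visit windowing rules".

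Protocol Table 8 allows -7 to +3 days for Day 29 and ±3 days for Day 15. Protocol Section 7 adds: "If a participant does not complete a visit within the time window, that visit will be classified as a missed visit". The Table 8 row "Blood for humoral immunogenicity" is marked in the unscheduled-visit column. On why such visits occur, Section 7 says: "An unscheduled visit may be prompted by reactogenicity issues, illness visit criteria for COVID-19, or new or ongoing AEs". Section 3.1 says that "participants may have blood sampled at unscheduled visits for acute respiratory symptoms", and Section 7.3.6 says: "Blood samples will be collected at all illness visits for potential future immunologic assessment of SARS-CoV-2 infection". Section 7.1 also permits repeat or unscheduled samples for safety or technical reasons.

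SAP Section 5.4 requires PPIS members to "have pre-booster and Day 29 neutralizing antibody data against prototype virus strain" and sets no day limits. Section 5.5 defines PPIS-Neg, the primary immunogenicity set, by the absence of infection on or before the booster. Section 6.4.2 names a subset with no infection up to Day 29 or Day 91, but only as an optional sensitivity analysis.

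**The concern.** The primary immunogenicity endpoint is meant to describe the response 28 days after the booster. Step 2 can replace a missing value with one drawn up to 58 days after it (59 - 1), and the visit that produced the sample may have been prompted by SARS-CoV-2 infection. Such a titre may be raised by infection, or lower than the Day 29 value because of waning.

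The affected quantities are the Day 29 GMT, GMFR and SRR in each arm and the ratios between arms. The same sample can also create eligibility: a participant with no scheduled Day 29 result enters PPIS because of it.

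The error need not be equal across arms. In Part A, an arm with more breakthrough infections would have more opportunities for substitution. In Part B the two dose arms are enrolled sequentially (SAP Section 4.3), so exposure to circulating virus may differ between them.

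**Working it through.** **1. The SAP window.** Table 3 places its limits at midpoints between target days: (15 + 29)/2 = 22 and (29 + 91)/2 = 60. The days strictly between are 23 to 59, which reproduces the stated Day 29 range. Its length is 59 - 23 + 1 = 37 days.

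**2. The protocol window.** For Day 29: 29 - 7 = 22 to 29 + 3 = 32, which is 11 days. For Day 15: 12 to 18. The SAP's upper limit for Day 29 is 59 - 32 = 27 days later than the protocol's.

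**3. One participant followed through the text.** A participant is SARS-CoV-2 negative at the booster, has no scheduled Day 29 sample, and attends an illness visit with COVID-19 on Day 50.

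| Rule | Result |
|---|---|
| Protocol Table 8, unscheduled visit | humoral blood is scheduled |
| SAP Appendix B, Step 2; 50 lies in 23 to 59 | the sample becomes the Day 29 value |
| SAP 5.4, Day 29 neutralizing antibody data | met by that sample |
| SAP 5.5, infection on or before the booster | none, so the participant stays in PPIS-Neg |
| SAP 6.4.2, infection-free subset | optional; outcome depends on its reading |

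On the last row, if Day 29 means study day 29, the Day 50 infection passes that version of the subset and only the Day 91 version removes it. If it means the analysis visit (2 to 59 for swabs and serology in Table 3), both versions remove it. The SAP does not say which applies.

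**4. Size, on assumed inputs.** Suppose k of n values in an arm are F times their true Day 29 level. The arm GMT is multiplied by F^(k/n). With n = 70, the planned maximum per arm:

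| k | F = 0.5 | F = 4 | F = 10 |
|---|---|---|---|
| 1 | 0.99 | 1.02 | 1.03 |
| 3 | 0.97 | 1.06 | 1.10 |
| 7 | 0.93 | 1.15 | 1.26 |

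For example, 4^(3/70) = 1.061. The ratio to an unaffected comparator moves by about the same factor. The documents give neither k nor F.

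**5. Seroresponse.** If a substituted value turns one true non-responder into a responder, SRR rises by 1/70 = 1.4 points. Compared with leaving the value missing, adding one responder to 69 others with rate p raises SRR by (1 - p)/70. That is 0.29 points at p = 0.8 and 0.14 points at p = 0.9 (both rates assumed).

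**The case against.** **Conflict with the protocol.** A reader might infer that the SAP contradicts the protocol, because the protocol calls a late visit missed. The documents do not support that. The protocol sentence governs site conduct and does not say which samples may be analysed. Contiguous midpoint windows wider than visit windows are not in themselves an error.

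**Other protection.** The optional infection-free subset is not the only possible safeguard. PPIS excludes major deviations affecting key data, and SAP Section 6.2.6 leaves those rules to be finalized before database lock. SAP Section 6.7 locks primary-analysis data through Day 29, which might leave a Day 50 sample out. Both points stand as possibilities. But the deviation rules are not written, and a sample missed by the primary lock could still enter the final analysis, so that the Day 29 results differ between the two.

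**Not every unscheduled sample is an illness sample.** Reactogenicity, other adverse events and technical redraws are also foreseen, and a redraw is a proper use of Step 2. The stated purpose of illness-visit blood is potential future assessment, so it might never be assayed for this endpoint. Table 8, however, lists humoral blood at unscheduled visits without that limit.

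**Scale.** Substitution needs a missing scheduled sample, and the sample nearest the target is preferred. Counting window days (27 of 37 beyond the protocol limit) says nothing about how many samples are affected. Illness visits are arranged promptly, so an early sample may show little infection-related rise.

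**Other routes.** Someone infected on Day 15 who gives a nominal Day 29 sample is also affected, whatever the window. That follows from how PPIS-Neg is defined, and narrowing the window would not cure it.

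**Conclusion.** The concern holds in a limited form. Followed exactly, the plan can take a titre drawn during infection, up to Day 59, as the primary Day 29 value, and can let that sample admit the participant to PPIS. No rule now written clearly prevents either result.

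The weakness is the combination of a wide window, illness-visit samples as permitted substitutes, and a primary set blind to infection after the booster.

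The effect is probably small: about 2% on an arm's GMT for one fourfold value in 70, and about 10% for three tenfold values. These sizes rest on assumed k and F. The comparisons are descriptive and no hypothesis is tested, so no error rate is at stake. It is an inexpensive improvement worth making before the lock.

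**What to change.** In SAP Appendix B:

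- State that samples drawn at illness visits, for suspected or confirmed SARS-CoV-2 infection, are never mapped to a scheduled humoral immunogenicity visit and do not satisfy the PPIS Day 29 condition. Repeat the second part in SAP Section 5.4.
- For the primary analysis, accept other unscheduled substitutes, such as technical redraws, only on Days 12 to 18 for Day 15 and Days 22 to 32 for Day 29. This also stops an unscheduled Day 2 sample from standing in for Day 15, and places an unscheduled Day 22 sample in Day 29, as in the protocol.
- Keep the Table 3 windows for a sensitivity table.
- Leave nominal scheduled samples under Step 1 as planned. Discarding every nominal sample outside Days 22 to 32 is a separate and debatable trade-off that this point does not require.

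The cost is a few sentences, plus the need to identify in the data which unscheduled visits were illness visits. A few participants lose a Day 29 value and leave PPIS. Their exclusion would depend partly on an event after the booster, so the sensitivity table is worth keeping alongside the primary result.
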